2.2.4. CCI

[figure not shown]
CCI

2.2.5. Nonclinical Safety

[figure not shown]
PF-07853578 was evaluated in GLP-compliant repeat-dose general toxicity studies up to 2 weeks in duration in rats and dogs, in vitro and in vivo genetic toxicity studies, and safety pharmacology studies in rats for assessment of neurofunctional and pulmonary effects or dogs for cardiovascular effects.

PF-07853578 was not mutagenic, aneugenic or clastogenic. In the single-dose safety pharmacology studies, CCI

CCI effects were noted in rats, and a NOEL was established in these studies.

In the 2-week GLP repeat-dose toxicity studies, CCI

CCI The NOAELs in the GLP toxicity studies were established at 1000 mg/kg/day in rats and dogs. In rats, the NOAEL corresponded to a total C_{max} of CCI

In summary, the nonclinical safety profile of PF-07853578 has been adequately characterized and supports progression into clinical trials of up to 14 days in duration. Additional details of the nonclinical safety program are provided in the IB.

2.3. Benefit/Risk Assessment

Study C5161001 is the first time that PF-07853578 will be administered to humans and is designed primarily to generate safety, tolerability, and PK data for further clinical development. PF-07853578 is not expected to provide any clinical benefit to healthy participants. The purpose of this study is to provide the basis for further clinical development of PF-07853578 as a first-in-class therapy for treatment of NASH with liver fibrosis in patients who are carriers of the PNPLA3-148M allele. As of the date of this protocol, no

specific human risks have been identified; postulated risks based on nonclinical studies are summarized in [Section 2.2.5](#). The clinical impact of these potential risks will be minimized with precautionary sentinel dosing and through the proposed cautious dose-escalation process wherein higher doses of PF-07853578 will be administered only after lower doses have been found to be well tolerated with an acceptable safety profile. In addition, this study will employ stopping rules for dose escalation ([Section 6.6.1](#)) and includes standard, intensive, inpatient monitoring of the participants following dose administration as outlined in the [SoA](#).

More detailed information about the known and expected benefits and risks and reasonably expected AEs of PF-07853578 may be found in the IB, which is the SRSD for this study. Refer to the Study Intervention(s) table in [Section 6.1](#) for a complete description of SRSDs.

2.3.1. Risk Assessment

Potential Risk of Clinical Significance	Summary of Data/Rationale for Risk	Mitigation Strategy
Study Intervention(s) PF-07853578		
Potential off-target adverse effects	PF-07853578 is a CCI [REDACTED], CCI [REDACTED]. Off-target interactions identified CCI [REDACTED] may include CCI [REDACTED] at high concentrations.	
During the study, participants will be in a closely monitored environment while in the CRU.Human exposures within the planned dose range are projected to all be below concentrations CCI [REDACTED]Precautionary sentinel dosing will be used in this study.Neurologic exams vital signs, ECG chemistries, and fasting lipids will be incorporated as part of safety monitoring.Smaller dose escalation steps may be implemented if clinically significant safety parameter changes are observed.
Drug-drug interactions resulting in exposure changes of background concomitant medications	At the dose range planned for the current study, PF-07853578 has the potential to elicit CCI [REDACTED].	
Use of prescription or nonprescription drugs and dietary and herbal supplements will be prohibited within 7 days or 5 half-lives (whichever is longer) prior to the first dose of study intervention through the last PK collection.
Drug-drug interactions resulting in PF-07853578 exposure changes	CCI [REDACTED] was responsible for a majority of the metabolism of PF-07853578 in vitro .	
Use of prescription or nonprescription drugs and dietary and herbal supplements that are moderate or strong CCI [REDACTED] inducers or inhibitors are prohibited within 14 days plus 5 half-lives prior to the first dose of study intervention through the last PK collection.
Effects on lipids	CCI [REDACTED] were seen in 14-day GLP toxicology studies with PF-07853578 in rats and dogs.	
Fasting lipid panels will be included as part of the clinical safety labs.
Effects on ovaries and adrenals	In 14-day GLP toxicology studies with PF-07853578, CCI [REDACTED] was seen in female rats, and mild-moderate vacuolation of adrenal	
WOCBP will be excluded from the study.Vital signs and electrolytes in standard clinical safety labs will be performed serially to monitor for signs of adrenal insufficiency.

PFIZER CONFIDENTIAL

CT02-GSOP Clinical Pharmacology Protocol Template (14 April 2023)

Page 24

Potential Risk of Clinical Significance	Summary of Data/Rationale for Risk	Mitigation Strategy
Study Intervention(s) PF-07853578		
	glands was seen in female and male rats.	
Effects on the liver	Non-adverse increases in liver weight and hepatocyte hypertrophy were seen in rats, and increased ALT in female dogs with PF-07853578 in 14-day GLP toxicology studies.	
Serial liver function tests will be measured as part of standard clinical safety labs.
Effects on pulmonary function	CCI [REDACTED] were seen in rats with PF-07853578 in single-dose safety pharmacology studies.	
Respiratory rate will be assessed serially as part of safety monitoring.

2.3.2. Benefit Assessment

The participants in this study are not expected to obtain any specific benefit beyond contributing to the process of developing new therapies in an area of unmet need. They will receive close monitoring of their safety via study procedures undertaken (eg, PEs, 12-lead ECGs, vital signs) which will occur as outlined in this protocol.

2.3.3. Overall Benefit/Risk Conclusion

Based on the totality of available nonclinical data and taking into account the measures to minimize risk to study participants, the overall benefit/risk profile supports clinical testing of PF-07853578 in this study as part of the clinical development for the treatment of NASH with liver fibrosis in patients who are carriers of the PNPLA3-148M allele.

3. OBJECTIVES AND ENDPOINTS

Objectives	Endpoints
Primary: 
To evaluate the safety and tolerability of single ascending doses of PF-07853578 administered orally to healthy adult participants.	Primary: 
Assessment of AEs, clinical safety laboratory tests, vital signs, continuous cardiac monitoring, 12-lead ECGs, PEs, and neurological examinations.
Secondary: 
To evaluate the PK of PF-07853578 following single doses of PF-07853578 administered orally to healthy adult participants.	Secondary: 
PK parameters derived from plasma PF-07853578 concentrations: C_{max}, T_{max}, AUC_{last}, and if data permit, AUC_{inf} and $t_{1/2}$.
Tertiary/Exploratory: 
To evaluate additional PK parameters of PF-07853578 following single doses of PF-07853578 administered orally to healthy adult participants.	Tertiary/Exploratory: 
Additional PK parameters derived from plasma PF-07853578 concentrations: $C_{max}(dn)$, $AUC_{last}(dn)$, and if data permit, $AUC_{inf}(dn)$, CL/F, and V_{d}/F.

To evaluate the effect of food on the PK of PF-07853578 following single doses of PF-07853578 administered orally to healthy adult participants (if conducted).	
PK parameters derived from plasma PF-07853578 concentrations after a high-fat/high-calorie meal: C_{max}, T_{max}, AUC_{last}, and if data permit, AUC_{inf} and $t_{1/2}$.

To evaluate the PK of PF-07853578 following single oral doses of an IDS oral solution of PF-07853578 administered orally to healthy adult participants (if conducted).	
PK parameters derived from plasma PF-07853578 concentrations after IDS oral solution dosing: C_{max}, T_{max}, AUC_{last}, and if data permit, AUC_{inf} and $t_{1/2}$.

4. STUDY DESIGN

4.1. Overall Design

This study is a randomized, investigator- and participant-blind, sponsor-open, placebo-controlled, FIH, single ascending dose, 4-period, crossover, interleaving design study of PF-07853578 orally administered to healthy adult participants. Approximately 24 healthy adult participants (up to 3 cohorts of approximately 8 participants each) will be enrolled in this study. The optional third cohort will only be used if the objectives of the study are not fulfilled in Cohort 1 and Cohort 2. Each participant is planned to undergo 4 treatment periods receiving up to 4 doses of PF-07853578 and up to 2 doses of placebo. In

PFIZER CONFIDENTIAL

CT02-GSOP Clinical Pharmacology Protocol Template (14 April 2023)

each period, participants will be randomized to either PF-07853578 or placebo in a ratio of 6:2. A diagram of the study design is shown in [Figure 1](#).

Precautionary sentinel dosing will be used in any period evaluating escalating doses of PF-07853578. Two participants (1 receiving PF-07853578 and 1 receiving placebo) within a period will be dosed initially before the remaining participants of that period are dosed. Safety and tolerability data through at least 24 hours post-dose for the sentinel participants will be reviewed prior to dosing the remaining participants of that period. Sentinel dosing may be omitted when repeating a dose level or administering a lower dose level than previously evaluated.

Screening activities will be completed over the 28 days prior to randomization in Period 1. In each period, participants will be admitted to the CRU on Day -1 and will remain in the CRU through at least the 72-hour assessments on Day 4. Participants may remain in the CRU after completion of Day 4 activities at the discretion of the investigator or if safety, tolerability, or PK data dictate the need to prolong confinement in the CRU. Participants will receive a single oral dose of PF-07853578 or placebo on Day 1 of each period. Dose levels will be escalated to bracket the expected clinical dose range, but the projected exposures will not exceed the predefined human exposure limits. Within an individual participant, there will be a washout interval of at least 10 days between doses. The total duration of participation from the screening visit to the telephone follow-up contact will be approximately 17 weeks for each participant. Participants will return for an on-site follow-up visit 7-10 days after the final dose of study intervention. The follow-up contact may occur via telephone contact and must occur 28-35 days after administration of the final dose of study intervention.

Dosing will occur in the fasted state for all periods, except if an optional exploratory assessment of the effect of food on PF-07853578 PK is conducted. If the food effect is evaluated, it is anticipated that study intervention will be administered in the fed state in the last period of Cohort 2 or Cohort 3 at a dose level that was previously administered fasted within the same cohort. However, study intervention may be administered in the fed state during any of the study periods/cohorts if thought necessary to achieve study objectives. The actual dose level will be selected based on emerging safety, tolerability, and PK data but will be expected to achieve approximate projected therapeutic exposures ([Section 4.3.2](#)).

If evaluated, the IDS oral solution of PF-07853578 is anticipated to be assessed in the last period of Cohort 2 or Cohort 3 at a dose level that was previously administered as a suspension within the same cohort. However, the IDS oral solution may be administered during any of the study periods/cohorts if thought necessary to achieve study objectives.

If a participant drops out before completing all study periods within a cohort or withdraws for a reason unrelated to the safety of the study intervention, the participant may be replaced at the discretion of the investigator and sponsor. The replacement participant(s) may or may not be required to complete all periods of the cohort in which they are participating at the discretion of the investigator and sponsor.

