6.3. Assignment to Study Intervention

The investigator will assign participant numbers to the participants as they are screened for the study. Pfizer will provide a randomization schedule to the investigator and, in accordance with the randomization numbers, the participant will receive the study treatment regimen assigned to the corresponding randomization number.

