9.5. Sample Size Determination

A sample size of approximately 24 healthy adult participants (up to 3 cohorts of approximately 8 participants each) has been chosen based on the need to minimize first exposure to humans of a new chemical entity and the requirement to provide adequate safety, tolerability, and PK assessment at each dose level. At each dose level, approximately 6 participants are planned to receive PF-07853578 and approximately 2 participants are planned to receive placebo with all participants at the end of the study having received up to 4 doses of PF-07853578 and up to 2 doses of placebo.

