2.3. Study Design

This study is a randomized, investigator- and participant-blind, sponsor-open, placebo-controlled, FIH, single ascending dose, 4-period, crossover, interleaving design study of PF-07853578 orally administered to healthy adult participants. Approximately 24 healthy adult participants (up to 3 cohorts of approximately 8 participants each) will be enrolled in this study. The optional third cohort will only be used if the objectives of the study are not fulfilled in Cohort 1 and Cohort 2. Each participant is planned to undergo 4 treatment periods receiving up to 4 doses of PF-07853578 and up to 2 doses of placebo. In each period, participants will be randomized to either PF-07853578 or placebo in a ratio of 6:2. A diagram of the study design is shown in Figure 1.

Precautionary sentinel dosing will be used in any period evaluating escalating doses of PF-07853578. Two participants (1 receiving PF-07853578 and 1 receiving placebo) within a period will be dosed initially before the remaining participants of that period are dosed. Safety and tolerability data through at least 24 hours post-dose for the sentinel participants will be reviewed prior to dosing the remaining participants of that period. Sentinel dosing may be omitted when repeating a dose level or administering a lower dose level than previously evaluated.

Figure 1. Study Design: Interleaving, Placebo-Controlled, 4-Period, Crossover Design

- Each period will consist of admission on Day -1, dosing on Day 1, and discharge at approximately 72 hours post-dose. Within a participant, there will be a washout interval of ≥10 days between doses.
- In each period, 6 participants will be randomized to receive PF-07853578, and 2 participants will be randomized to receive matching placebo.
- Precautionary sentinel dosing will be employed. Two participants (1 receiving PF-07853578 and 1 receiving placebo) within a period will be dosed initially before the
 remaining participants of that period are dosed. Safety and tolerability data through at least 24 hours post-dose for the sentinel participants will be reviewed prior to dosing
 the remaining participants of that period. Sentinel dosing may be omitted when repeating a dose level or administering a lower dose level than previously evaluated.

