5.2. General Methods

Unless otherwise stated, all summaries and plots will be presented by dose and treatment as applicable. Each formulation of PF-07853578 administered during the study and fasting status will be considered as separate treatments.

Unless otherwise stated the summary tables and/or statistical analyses will only include a single pooled placebo group across all included cohorts. Placebo will be pooled from all dose escalation periods but not for the fed period (if conducted) and for IDS oral solution period (if conducted).

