6.3.2. Plasma PF-07853578 PK Parameters During Food Effect Period (if conducted)

Plasma PK parameters for PF-07853578 on Fed State as described in Section 3.3.2 will be listed and summarized descriptively as described in Section 6.2 for participants in the PK Parameter Set as defined in Section 4.

Natural loge transformed AUC_{inf} (as data permit), AUC_{last}, and C_{max} (dose-normalized prior to analysis, if appropriate) of PF-07853578 on fasted state or on fed state will be analyzed using a mixed effect model as described in Section 5.2.3, using only data from the respective periods that includes the two treatments of interest. The test treatment will be PF-07853578 administered with food in comparison to the reference treatment of PF-07853578 administered on fasted state.

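### Should the plan require a fed or IDS period to keep the active/placebo allocation of its reference period?

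*Protocol*

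**What the plan says.** Protocol 4.1 sets the allocation period by period: "each period, participants will be randomized to either PF-07853578 or placebo", at 6:2. SAP 2.3 repeats it. Each participant has four periods, and Protocol 9.5 describes "all participants at the end of the study having received up to 4 doses of PF-07853578 and up to 2 doses of placebo".

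The food assessment is optional. It is expected in the last period of Cohort 2 or 3, "at a dose level that was previously administered fasted within the same cohort"; the IDS solution is handled the same way with the suspension as reference. Protocol 4.1 also lets either assessment be placed in any period or cohort.

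The order of treatments comes from a schedule supplied by the sponsor. Under Protocol 6.3, "the participant will receive the study treatment regimen assigned to the corresponding randomization number". The structure of that schedule is not described, and the graphic of Figure 1, to which Protocol 4.1 refers for the design, is not reproduced in the text available.

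SAP 5.2 keeps placebo from a fed or IDS period out of the pooled placebo group, so placebo is expected in those periods. SAP 5.2.3 fits treatment as a fixed effect and participant as a random effect. SAP 6.3.2 applies this model "using only data from the respective periods that includes the two treatments of interest", and SAP 6.3.3 does the same for the IDS solution.

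**The concern.** A food or formulation ratio is most precise when the same people take the drug in both periods, because differences between participants then cancel. Repeating a dose within a cohort invites that comparison, but the text fixes only the dose and the cohort. Read literally, a 6:2 randomization in each period could give placebo in the fed period to someone who was active in the reference period, and the reverse. Each such participant contributes one active observation, which carries mostly between-participant information. For the same number of doses the ratio would be estimated less precisely, and a sentence on carrying the allocation over would seem to prevent this cheaply.

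**Working it through.** **The plan's own figure.** Three cohorts of 6 + 2 give 3 × 8 = 24, as stated. The size is not based on power, and no number of pairs is given.

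**Number of pairs.** Inputs: 8 participants, 2 on placebo in each period (Protocol 4.1). There are C(8,2) = 28 possible placebo pairs. Hold the reference pair fixed and draw the second independently:

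| Overlap of the placebo pairs | Active/active pairs | Probability |
|---|---|---|
| both the same | 6 | 1/28 = 3.6% |
| one shared | 5 | 12/28 = 42.9% |
| none shared | 4 | 15/28 = 53.6% |

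The mean is 4.5, and the probability of fewer than 6 is 27/28 = 96.4%. There can never be fewer than 8 − 2 − 2 = 4.

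Fully independent draws are not quite the stated design, because no participant may have more than two placebo doses. Of the 28⁴ = 614,656 four-period allocations, 380,100 respect that limit; the other 38% break it. If all permitted allocations are equally likely, the probabilities of 4, 5 and 6 pairs are 65.6%, 32.7% and 1.7%, so fewer than 6 has probability 98.3% and the mean is 4.36. If every participant receives placebo exactly once, there are always 4 pairs.

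**Loss of precision.** Let p be the number of pairs and u = 6 − p the number of unpaired active participants in each period. With known variance components, the model in SAP 5.2.3 gives

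Var(log ratio) = 2 / [p/σw² + u/(σb² + σw²)].

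Relative to 6 pairs the variance ratio is 6 / (p + u·r), with r = σw²/(σb² + σw²) and σ² = ln(1 + CV²). The documents give no CVs; I assume 30–50% between and 20–30% within participants.

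| CV between / within | r | Variance ratio, 5 pairs | Variance ratio, 4 pairs |
|---|---|---|---|
| 30% / 30% | 0.500 | 6/5.500 = 1.09 | 6/5.000 = 1.20 |
| 40% / 30% | 0.367 | 6/5.367 = 1.12 | 6/4.735 = 1.27 |
| 50% / 20% | 0.149 | 6/5.149 = 1.17 | 6/4.299 = 1.40 |

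At 40%/30% the standard errors are 0.1695 (6 pairs), 0.1792 (5) and 0.1908 (4). Taking square roots of the variance ratios and weighting by the probabilities:

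- Independent draws, 30%/30%: 0.536 × 1.095 + 0.429 × 1.044 + 0.036 × 1 = 1.07. At 50%/20% the result is 1.13.
- Two-placebo limit, 30%/30%: 0.656 × 1.095 + 0.327 × 1.044 + 0.017 × 1 = 1.08. At 50%/20%: 0.656 × 1.181 + 0.327 × 1.079 + 0.017 × 1 = 1.15.

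As a less favourable view, drop the unpaired participants. The 90% interval then multiplies and divides the ratio by exp[t(0.95, p − 1) · σw · √(2/p)]. At a within-participant CV of 30% this factor is 1.41 for 6 pairs, 1.49 for 5 and 1.63 for 4.

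**Do the dose limits fit matching?** Four periods with 2 placebo doses each make 8 doses for 8 people, so one each was possible. Suppose instead that three different placebo pairs are used in Periods 1 to 3 and Period 4 repeats its reference period. The placebo counts are then 2,2,1,1,1,1,0,0. The maxima are 2 placebo and 4 active doses, exactly the stated limits.

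**The case for a change.** The strongest case for a change is that the text really is silent, the arithmetic is right, and the crossover is justified in Protocol 4.2 partly by the within-participant comparisons it permits. The limits of 4 active and 2 placebo doses also fit unmatched schedules, so they do not prove that matching is intended. Matching has to be planned ahead: under independent draws only (15/28) × (6/28) = 11.5% of allocations leave nobody with two placebo doses after three periods. Sponsor staff are already unblinded for dose decisions, so a contingent schedule is workable.

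All of this stands as a reason to ask how the schedule is built. It does not stand as a reason to amend the plan, because a general carry-over rule is harder to write than it looks:

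- A fed or IDS period may fall in Period 2 or 3, where keeping the reference allocation gives two people a second placebo dose early. A companion rule of at most one placebo in the first three periods would then contradict it.
- If fed and IDS periods in one cohort were both matched to one reference period, the same two people would have three placebo doses, above the limit.
- Matching gives up fresh randomization in that period, so its safety comparison rests on the same two placebo participants.
- Stating the rule in the protocol tells blinded site staff that two periods share an assignment. A guess, or an emergency unblinding, in one period then carries over to the other.

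**Conclusion.** No change is needed. What is unstated is a detail of the randomization schedule, which the sponsor holds and can build sensibly once the reference dose is chosen. Neither that schedule nor the Figure 1 graphic is available here, so independent allocation cannot be taken as the design.

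If the periods turn out unmatched, a full cohort of 8 most likely gives 4 or 5 pairs instead of 6. The standard error rises by roughly 7–13% under independent-draw weights, or 8–15% if schedules within the two-placebo limit are equally likely. Those figures rest on assumed CVs, variance components treated as known, and no dropout; an analysis of complete pairs alone would lose more. The ratio itself stays valid: the mixed model handles unpaired participants, and at least four pairs remain. The assessments are optional and exploratory, the plan promises no number of pairs and no precision, and there is no hypothesis test. That loss is a fair trade against the blinding and scheduling costs of a written rule.

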An interleaving design will be employed in this study to spread PF-07853578 dose levels across a wide range within an individual participant and to reduce the risk of carryover effects on PK and the anticipated dynamics of PNPLA3 levels return to baseline across the planned dose/exposure range. The duration of time between the interleaving dose escalation periods in Cohort 1 and Cohort 2 will be determined by the time required for analysis and review of the safety, tolerability, and PK data from each dosing period before making a decision on the subsequent PF-07853578 dose level to be evaluated. Therefore, the duration of time between doses in an individual participant will be ≥ 10 days because at high doses of PF-07853578, PNPLA3 levels are predicted to return to baseline in ≤ 7 days.

Based on the predicted $t_{1/2}$ of PF-07853578, plasma concentrations of PF-07853578 are expected to be below the limit of detection in approximately 3 days, thus PK samples are planned to be collected over 72 hours post-dose. However, sampling times, duration of sampling, and/or the length of the interval between doses may be modified and/or extended based on emerging PK. The planned doses in the dose escalation sequence ([Table 3](#)) may be modified or repeated, as guided by emerging safety, tolerability, and PK data but will follow the dose-escalation rules defined in [Section 6.6.1](#).

Neurological examinations will be conducted **CCI**

[REDACTED] . Neurologic signs

will be monitored closely pre- and post-dose, and participants will remain in a closely monitored environment for 72 hours post-dose, which is deemed sufficient based on the predicted effective $t_{1/2}$ of PF-07853578.

Respiratory rate will be assessed CCI

A fasting lipid panel, consisting of total cholesterol, triglycerides, HDL, and direct LDL, will be monitored with clinical safety lab tests CCI

Food may increase PF-07853578 exposures, therefore an exploratory assessment of the effect of food on PF-07853578 PK may be conducted to confirm *in silico* predictions.

CCI

PGx blood samples will be collected for retrospective genotyping of PNPLA3 polymorphism (rs738409) in each participant. This data may enable assessments of differential safety, tolerability, and PK by genotype and may inform the design of subsequent clinical studies with PF-07853578. The results of such analyses are not planned to be included in the CSR.

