4.3.4. Rationale for Dose Selection

The safety, tolerability, and plasma PK of PF-07853578 after administration of single escalating oral doses across a wide dose/exposure range will be evaluated in this study. Dosing will occur in the fasted state, except in periods in which dosing may occur in the fed state to permit exploratory assessment of the effect of food on PF-07853578 PK. The doses presented in Table 3 are projected based on nonclinical data and may be modified based on emerging observed human safety, tolerability, and PK data generated during this study. The initial range of planned doses in this study were established using toxicokinetic data, predicted human PK parameter estimates, projected PNPLA3 reduction, and projected efficacious concentrations.

Table 3. Predicted Human Exposures, Projected Liver PNPLA3 Reduction, and Safety Margins at Proposed Single Doses of PF-07853578

Dose (mg)	CCl
1	
3	
10	
30	
75	
150	
300	
CCl	

A PF-07853578 starting dose level of 1 mg is planned. This starting dose level was informed by CCl

and was selected to achieve projected minimal PD activity. At a single dose of 1 mg, PF-07853578 exposures are projected to be well below exposures associated with efficacy and the human exposure limits. CCl

are projected to be reduced by approximately CCl, respectively, at C_{max} , suggesting minimal PD activity. The predicted C_{max} and C_{av} are:

CCl

- CCl, below the human exposure limits defined for PF-07853578 dose escalation in [Section 4.3.3](#).

The dose range to be studied was selected to account for uncertainties in the projected C_{eff} and the projected therapeutic dose, while also bracketing the expected clinically effective dose range in humans for clinically relevant pharmacological activity and providing safety coverage for a wide range of PF-07853578 doses.

Assessment of the safety, tolerability, and PK after each single dose level will be conducted before escalating to the next dose level. The dose/exposure-escalation increments are planned

to be up to approximate semi-logarithmic increases in exposure from the previous highest dose level that has been evaluated. If exposure exceeds the projected therapeutic range, or if changes in safety parameters are observed, smaller dose-escalation steps may be implemented.

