The actual dose levels, target exposures, and/or dose level increments may be adjusted (higher or lower) during the study based on emerging human safety, tolerability, and PK data, but projected exposures will not exceed the predefined human exposure limits. Dose levels may also be repeated if warranted.

When the assessment of the effect of food on the PK of PF-07853578 is conducted, the dose level will be selected based on emerging safety, tolerability, and PK data from previous periods of this study. The actual dose level used will be expected to achieve exposures similar to or greater than projected therapeutic exposures (as outlined in [Section 4.3.2](#)).

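### The sentinel waiver goes by nominal dose, so a first fed or first IDS-solution period at a repeated dose needs no sentinel pair even if it gives the highest exposure so far

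*Protocol*

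**What the plan says.** **When sentinels are required.** Protocol 4.1: "Precautionary sentinel dosing will be used in any period evaluating escalating doses of PF-07853578". The pair is one participant on active drug and one on placebo, with at least 24 hours of review before the others are dosed.

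**When they may be dropped.** Protocol 4.1: "Sentinel dosing may be omitted when repeating a dose level or administering a lower dose level than previously evaluated". Protocol 1.1 and 6.6 repeat this sentence. SAP 2.3 carries it in the body text and in the notes to Figure 1. None of these places mentions exposure, fasting condition or formulation.

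**The fed period.** It is optional. Section 4.1 anticipates it in the last period of Cohort 2 or 3, "at a dose level that was previously administered fasted within the same cohort", but adds that "study intervention may be administered in the fed state during any of the study periods/cohorts if thought necessary to achieve study objectives". On the dose, 4.1 says "but will be expected to achieve approximate projected therapeutic exposures", whereas 4.3.4 says "The actual dose level used will be expected to achieve exposures similar to or greater than projected therapeutic exposures". Section 4.2 gives the reason for the period: "Food may increase PF-07853578 exposures, therefore an exploratory assessment of the effect of food on PF-07853578 PK may be conducted".

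**The IDS oral solution period.** It is also optional. It is anticipated at a dose already given as suspension in the same cohort, with the same freedom to move it to another period or cohort.

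**How escalation is measured.** Section 4.3.4 plans the increments "to be up to approximate semi-logarithmic increases in exposure from the previous highest dose level that has been evaluated". The stopping rules in 6.6.1 are on mean exposure.

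**The concern.** Step sizes and stopping limits are framed in exposure, but the rule for staging the first exposed participants is framed in milligrams. On plain wording, a fed repeat of a fasted dose, or a solution repeat of a suspension dose, counts as a repeated dose level. The sentinel requirement is then not triggered and the waiver is available.

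If food or the new formulation raised concentrations enough, a whole group could reach the highest exposure yet seen in humans in one step. The same rise produced by a larger dose would be sentinel-dosed. The risk table in 2.3.1 places possible off-target effects at high concentrations and lists sentinel dosing as a mitigation, so the safeguard should follow concentration.

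**Working it through.** The plan gives no figure to reproduce. The check is a reading of the rule followed by a break-even calculation.

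**1. Does anything else require sentinels in these periods?** No sentence does. Section 6.6 says sentinel dosing will be used in the study, then repeats the waiver. SAP 5.2 treats fasting status and formulation as separate treatments, but only for summaries and analyses.

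**2. When would a fed repeat set a new maximum?** Inputs: the Table 3 doses (1, 3, 10, 30, 75, 150 and 300 mg). Assumption: exposure is proportional to dose^b, with b = 1 for dose proportionality. The break-even fed/fasted ratio is

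R* = (highest fasted dose given / fed dose)^b

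| Fed dose | Highest fasted dose | R* (b = 1) |
|---|---|---|
| 300 mg | 300 mg | 300/300 = 1.0 |
| 150 mg | 150 mg | 150/150 = 1.0 |
| 150 mg | 300 mg | 300/150 = 2.0 |
| 75 mg | 300 mg | 300/75 = 4.0 |
| 30 mg | 300 mg | 300/30 = 10 |

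If exposure rises less than proportionally, say b = 0.7 (assumed), the 2.0 threshold becomes 2^0.7 = 1.62. The same formula applies to the IDS solution with the solution/suspension ratio in place of the food ratio. The documents give neither ratio.

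**3. Which row is plausible under the anticipated plan?** Seven dose levels fit in 2 × 4 = 8 periods. If the cohorts alternate (assumed, since Figure 1 is not shown), Cohort 1 takes 1, 10, 75 and 300 mg. Cohort 2 takes 3, 30 and 150 mg and has its last period free. A same-cohort fed period in Cohort 2 after 300 mg then has its lowest threshold at 150 mg: food would have to more than double exposure.

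A threshold of 1.0 needs one of two departures:
- escalation ends at 150 mg for a reason other than exposure or tolerability, and Cohort 2 then repeats 150 mg fed; or
- the highest dose is repeated fed elsewhere, most plausibly in the optional Cohort 3.

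**4. How large is a food effect at the top dose in the plan's own terms?** A 2-fold effect on a repeated top dose equals the planned 150 to 300 mg step (300/150 = 2), which does require sentinels. It is below the semi-logarithmic ceiling of 10^0.5 = 3.16.

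**5. Who is exposed before the first 24-hour review?** Allocation is 6 active to 2 placebo per period. With the waiver, up to 6 participants on active drug are dosed; with sentinels, 1.

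**6. How many of the 6 have had that dose before?** In the anticipated same-cohort design, 6 of 8 received it in the earlier period and 6 of 8 receive it now. The overlap is at least 6 + 6 − 8 = 4, absent replacements.

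**The case against.** The strongest case is that several optional conditions must coincide. The fed and IDS periods may never run, and the waiver is permissive. Section 4.1 expects roughly therapeutic exposure in the fed period. Because the doses are meant to bracket the clinical range, such a dose should lie below the top if escalation goes as planned.

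Other controls also remain:
- Section 6.6 requires review of PK and safety data before any increase, decrease or repeat.
- Sections 4.3.4 and 6.6.1 bar doses projected above the limits, and 6.6.1 conditions progression on the last dose having been well tolerated. If escalation stopped for exposure or tolerability, these rules also constrain a fed repeat at that dose.
- Most of the fed group would already have had that dose, with their own data in hand.
- Since 4.3.4 treats dose and exposure escalation together, one can argue that a fed period projected above the previous maximum is not a mere repeat.

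Most of this stands, and it keeps the point small. It does not close the gap. The limits also apply to every dose increase, where sentinels are still required. The 6.6 review looks at exposures already reached, not at the new one. Earlier experience of the dose fasted, or as suspension, is not experience of a higher concentration. The argument about what counts as a repeat shows that the text needs a clarifying sentence.

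**Conclusion.** The point holds as a narrow gap. At a repeated dose, the first fed or first IDS-solution period may be run without sentinels even if it yields the highest exposure so far, below the limits. It matters when the dose is at or near the highest given: break-even ratio 1.0 at the top dose and 2.0 for 150 mg after 300 mg. At 30 mg after 300 mg (ratio 10) it is remote. These thresholds assume dose proportionality.

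Three stronger readings are tempting and are not supported:
- *The plan would let participants exceed the exposure limits.* It would not; projected exposure is capped.
- *Six participants new to that dose would be exposed at once.* In the anticipated design at least 4 of the 6 have had it. The count of 6 against 1 concerns exposure before a 24-hour review, not first experience of the dose.
- *A new maximum in a fed period is likely.* This cannot be judged: the food ratio is not given, and the therapeutic dose and limits are redacted. For the IDS solution the documents give not even an expected direction.

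Severity is low to moderate: a cheap improvement, best made before any fed or IDS period.

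**What to change.** Replace the waiver sentence in Protocol 1.1, 4.1 and 6.6 and in SAP 2.3, including the Figure 1 notes, with wording such as:

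> The sentinel step may be dropped for a repeated or lower dose level given under the same fasting condition and in the same formulation. For the first fed period or the first IDS solution period, it may be dropped only if projected mean Cmax and AUC, using a conservative (upper-end) estimate of the food or formulation ratio, do not exceed the highest mean exposure already reviewed as well tolerated. Otherwise the two-participant sentinel step with at least 24 hours of review applies.

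The upper-end estimate matters because the fed period exists partly to confirm an in silico prediction. A trigger based on the central prediction would waive sentinels in just the case where that prediction is too low.

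The cost is one amended rule, carried into each place above at the next amendment with IRB/EC approval. Section 6.6.1 already calls for projecting mean Cmax and AUC for the next dose. Operationally it adds a pause of at least 24 hours, only if triggered. Section 8.1 already allows the remaining participants to be dosed after such a pause without repeating Day -1 procedures, provided no more than 48 hours separate Day -1 and Day 1.

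Aligning the fed-exposure target between 4.1 and 4.3.4 would be tidy but is editorial only.
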